- Recovered: Fully recovered or by medical or surgical treatment the condition has returned to the level observed at the first trial related activity after the subject signed the informed consent
- Recovering: The condition is improving and the subject is expected to recover from the event. This term should only be used when the subject has completed the trial
- Recovered with sequelae: As a result of the AE, the subject suffered persistent and significant disability/incapacity (e.g. became blind, deaf, paralysed). Any AE recovered with sequelae should be rated as an SAE
- Not recovered
- Fatal
- Unknown

Collection, Recording and Reporting of Adverse Events

All events meeting the definition of an adverse event will be collected and reported from the first trial related activity after the subject has signed the informed consent and until the end of the post-treatment follow-up period as stated in the protocol.

Follow-up of Adverse Events

During and following a subject's participation in a clinical trial, the sponsor-investigator and institution will provide adequate medical care to the study subject for any study-related adverse events, including clinically significant laboratory values related to the study. This medical care for study subjects will be provided regardless of their insurance status.

All adverse events classified as serious or severe or possibly/probably related to the trial product will be followed until the subject has recovered and all queries have been resolved. For cases of chronic conditions follow-up until the outcome category is "recovered" is not required, as these cases can be closed with an outcome of "recovering" or "not recovered". All other adverse events will be followed until the outcome of the event is "recovering" (for chronic conditions), or "recovered" or until the end of the post-treatment follow-up stated in the protocol, whichever comes first, and until all queries related to these AEs have been resolved.

Pregnancy

Study subjects will be instructed to notify the sponsor-investigator immediately if they become pregnant. The sponsor-investigator will report to Astra Zeneca any pregnancy occurring during the trial period. Reporting of pregnancy by sponsor-investigator will occur within the same timelines described above for reporting of Adverse Events. Pregnancy complications will be recorded as adverse event(s). If the infant has a congenital anomaly/birth defect this must be reported and followed up as a serious adverse event.

Precautions/Over-dosage

Precautions and procedures will be observed in the event of overdose of Dapagliflozin provided during the study.

REPORTING OF SERIOUS ADVERSE EVENTS

Investigators and other site personnel must inform the FDA, via a MedWatch/AdEERs form, of any serious or unexpected adverse events that occur in accordance with the reporting obligations of 21 CFR 312.32, and will concurrently forward all such reports to AZ. A copy of the MedWatch/AdEERs report must be faxed to AstraZeneca at the time the event is reported to the FDA. It is the responsibility of the investigator to compile all necessary information and ensure that the FDA receives a report according to the FDA reporting requirement timelines and to ensure that these reports are also submitted to AstraZeneca at the same time.

When reporting to AstraZeneca, a cover page should accompany the MedWatch/AdEERs form indicating the following:

- Investigator Sponsored Study (ISS)
- The investigator IND number assigned by the FDA
- The investigator's name and address
- The trial name/title and AstraZeneca ISS reference number

Investigative site must also indicate, either in the SAE report or the cover page, the causality of events in relation to all study medications and if the SAE is related to disease progression, as determined by the principal investigator.

Send SAE report and accompanying cover page by way of fax to AstraZeneca's designated fax line: [name]

Serious adverse events that do not require expedited reporting to the FDA need to be reported to AstraZeneca preferably using the MedDRA coding language for serious adverse events.

In the case of blinded trials, AstraZeneca will request that the Sponsor either provide a copy of the randomization code/ code break information or unblind those SAEs which require expedited reporting. All SAEs have to be reported to AstraZeneca, whether or not considered causally related to the investigational product. All SAEs will be documented. The investigator is responsible for informing the IRB and/or the Regulatory Authority of the SAE as per local requirements.

LIABILITY AND SUBJECT INSURANCE:

The sponsor-investigator should state that during and following a subject's participation in trial, the sponsor-investigator and his/her institution will provide adequate medical care to the study subject for any study-related adverse events, including clinically significant laboratory values related to the study. This medical care for study subjects will be provided regardless of their insurance status.

The sponsor-investigator will be responsible for the conduct of the study and agrees to defend, indemnify, and hold harmless Astra-Zeneca, any of its parent companies, affiliates, or subsidiaries, and their respective officers, directors, employees, agents, representatives, distributors, salespersons, customers, licensees, and end-users from and against any claim, suit, demand, loss, damage, expense or liability imposed by any third party arising from or related to: (a) any breach of sponsor-investigator's obligations; or (b) sponsor-investigator's negligent or grossly negligent use or willful misuse of the study drug, the results, or services derived there from. This indemnification shall not apply in the event and to the extent that a court of competent jurisdiction or a duly appointed arbiter determines that such losses or liability arose as a result of Astra-Zeneca gross negligence, intentional misconduct, or material breach of its responsibilities.

PUBLICATION PLAN:

Data generated from the study will be published in highly ranked peer reviewed scientific journals and presented at national and international meetings. Astra-Zeneca will have any manuscripts for publication for review with a right to comment.

The sponsor-investigator will register the study with a publicly assessable database such as clinicaltrials.gov.

REFERENCES:

1. [name] G, Bianco AC (2011). Epicardial adipose tissue: emerging physiological, pathophysiological and clinical features. *Trends Endocrinol Metab.* 2011 Aug 16

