- a) Dapagliflozin causes a rapid and significant reduction of EAT in type 2 diabetic patients
- b) Dapagliflozin-induced EAT reduction would be associated with a significant reduction of LV mass, independent cardiovascular risk factor.

ENDPOINTS:

Primary Endpoint: EAT (Epicardial fat thickness) will be measured with echocardiography according to the method described and validated by [name] et al. Full description of the measurement is reported in the section "Methodology"

Secondary Endpoint: LVM (left Ventricular Mass) will be measured with echocardiography according to the standard formula, fully described in the section "Methodology"

SPECIFIC OBJECTIVES

Primary Objective:

- a) Does treatment with Dapagliflozin cause a significant decrease in EAT in subjects with type 2 diabetes?

Secondary Objective:

- b) Does treatment with Dapagliflozin cause a significant decrease in LVM, through the reduction of EAT, in subjects with type 2 diabetes?

[figure not shown]
STUDY DESIGN

This will be an interventional, double-blind, parallel group, placebo controlled study in 100 overweight/obese type 2 diabetic subjects who are taking Metformin as monotherapy.

Individuals will be randomized in two groups of 50 patients, to receive additional Farxiga (Dapagliflozin) (F-group) or to remain on Metformin (M-group) plus placebo orally once daily.

[figure not shown]
- F-group: Dapagliflozin will be administered at the starting dose of 5 mg once daily, then if no safety issues will occur, it will be titrated up to 10mg once daily after 2 weeks. Metformin (from 500 mg twice daily to a maximum of 1000 mg twice daily) regimen will be continued to achieve fasting glucose between 80 and 140 mg/dl.
- M-group will be treated with Metformin plus placebo orally once daily for the duration of the study. Metformin (from 500 mg twice daily to a maximum of 1000 mg twice daily) regimen will be continued to achieve fasting glucose between 80 and 140 mg/dl.

Both groups will receive lifestyle and diabetes education, as part of the standard care.

STUDY TIMETABLE

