Participants will be scheduled for the first visit (visit 0) after an overnight fast. Patients will be randomly assigned to receive Farxiga 5 mg or placebo once daily. After 2 weeks patients will receive detailed instructions over the phone to titrate Farxiga or placebo up to 10 mg once daily. F- and M- group patients will undergo clinical examination, anthropometrics, transthoracic echocardiogram for EAT and LVM measurement and point of care (POCT) of fasting glucose and haemoglobinA1c (HbA1c) and estimated Glomerular Filtration Rate (eGFR) at each visit, baseline (visit t0), 3 (visit t3), and 6 months (visit t6)

STUDY POPULATION

Number of subjects to be studied: One hundred overweight/obese type 2 diabetic subjects.

Planned number of subjects to be screened: Five hundred subjects will be screened among the outpatient population who routinely refer to [name] of Miami Diabetes Clinic at the Diabetes Research Institute (UMMG-DRI), out-patient clinics. [name] visits approximately 2000 diabetic patients per year.

Anticipated number of trial sites: UMMG-DRI out-patient diabetes clinics, University of Miami.

INCLUSION CRITERIA

- Type 2 diabetes, as defined by ADA criteria
- HbA1c < 8% measured at least 1 week prior to the study
- BMI ≥ 27 kg/m²
- Pre-treatment with Metformin as monotherapy
- Age > 18 and < 65 years old
- Normal and stable hemodynamic status

EXCLUSION CRITERIA

- Known contra-indications to Farxiga, in accordance with risks and safety information included in the latest updated Prescribing Information
- Type 1 diabetes, as defined by American Diabetes Association (ADA) criteria
- Insulin dependent or treated type 2 diabetes
- Current use of other SGLT2 inhibitors, GLP- 1 analogs or DPP4 inhibitors
- Glomerular Filtration Rate (GFR) < 60 mL/min/1.73 m²
- Signs or symptoms of hypovolemia
- Patients with poor glycemic control (HbA1c ≥ 8%) will be excluded to maximize long-term patient retention without need
- History of diabetes ketoacidosis
- Patients with active bladder cancer or with a prior history of bladder cancer
- Acute or chronic infective, including genital mycotic infections
- Clinical signs or symptoms of New York Heart Association (NYHA) class III-IV heart failure
- Clinical or laboratory evidences of chronic active liver diseases
- Acute or chronic infective diseases
- Cancer or chemotherapy
- Current use of systemic corticosteroids or in the 3 months prior this study

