- Known or suspected allergy to Dapagliflozin, excipients, or related products
- Pregnant, breast-feeding or the intention of becoming pregnant
- Females of childbearing potential who are not using adequate contraceptive methods

Withdrawal Criteria

Study subject may withdraw at will at any time.

Repeated eGFR <60 mL/min/1.73 m² and hypoglycaemic (< 70 mg/dl) episodes will mandate discontinuation of the patient from the study.

VISIT PROCEDURES

Once patient eligibility and written consent are obtained, the participant is then scheduled for the baseline (t0) clinic visit through the University of Miami UChart (Epic) electronic system. The visits will be coordinated by the research coordinator. Each patient will undergo a baseline echocardiographic study for the measurement of EAT and LVM. Each patient will also have a full physical examination, body weight, height, waist and hip circumference measured, a point of care of fasting glucose and haemoglobinA1c (HbA1c). Echocardiographic study will be performed on site by [name] and by an experienced cardiac imaging technician who will be trained to measure echocardiographic EAT by [name]. The same visit procedures will be repeated after 3 (t3) and 6 (t6) months.

DESCRIPTION OF STUDY SITE

UM Miller School of Medicine has been the site of several National Institutes of Health studies and many peer-reviewed, epidemiologic and health services research publication. The Division of EDM is fully equipped and trained to visit, follow up and manage patients with diabetes. UMMG-DRI is fully accredited and equipped to perform state-of-the-art diagnostic tests assisting in the diagnosis and management of diabetes. The Division is also equipped with a state-of-the-art echocardiographic unit, Siemens, Acuson, USA, for the measurement of the EAT. [name] pioneered the echocardiographic measurement of the epicardial fat and he is considered the leading expert in epicardial fat research

METHODOLOGY

Informed consent will be in place before any study related procedures will be conducted.

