Fasting point of care tests will be obtained from all individuals according to the study design timetable. Blood parameters will be measured according to standard and previously described procedures.

Follow up of glucose profile Study patients will be advised to monitor their capillary glucose twice daily, fasting in the morning and post-prandially. Glucose profile will be tracked weekly by the research coordinator using myUhealth, a new and convenient UM online method of communication with the sponsor investigator, or by telephone. Research coordinator will inform the sponsor investigator on patients' glucose readings.

COMPLIANCE AND RETENTION STRATEGY We estimate that the majority of the participants who will be considered eligible will complete the study. Attrition can be estimated as lower than 10%. In the event that participants are lost to follow-up, the research coordinator will contact with the study participant by telephone. The research coordinator will be trained in effective telephone technique to maximize recruitment success.

STATISTICAL CONSIDERATIONS:

[name]' group previously showed and published that epicardial fat thickness decreased from 12.3 ± 1.8 to 8.3 ± 1 mm $P < 0.001$ after the 6-month very low calorie diet, accounting for a 32% reduction from the baseline. Average weight loss after the 6-month VLCD in those morbidly obese subjects was approximately 20 kg. It has been reported that Dapagliflozin can cause an approximately 1.5 kg decrease of body weight.

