A clinical laboratory AE is any clinical laboratory abnormality regarded as clinically significant i.e. an abnormality that suggests a disease and/or organ toxicity and is of a severity, which requires active management, (i.e. change of dose, discontinuation of trial product, more frequent follow-up or diagnostic investigation).

Serious Adverse Event (SAE):

A serious AE is an experience that at any dose results in any of the following:

- Death
- A life-threatening* experience
- In-patient hospitalization or prolongation of existing hospitalization
- A persistent or significant disability/incapacity
- A congenital anomaly/birth defect
- Important medical events that may not result in death, be life-threatening*, or require hospitalisation may be considered an SAE when, based upon appropriate medical judgement, they may jeopardise the subject and may require medical or surgical intervention to prevent one of the outcomes listed in this definition

*The term life-threatening in the definition of SAE refers to an event in which the subject was at risk of death at the time of the event. It does not refer to an event which hypothetically might have caused death if it was more severe.

Serious Adverse Drug Reaction (SADR):

An adverse drug reaction (ADR) is an adverse event for which a causal relationship (Possible/Probable relation) between the study drug and the occurrence of the event is suspected. The ADR should be classified as **serious** if it meets one or more of the seriousness criteria.

Medical Events of Special Interest (MESI): A MESI is (1) a medication error (e.g. wrong drug administration or wrong route of administration) or (2) a suspected transmission of an infectious agent via the product

Non-Serious Adverse Event:

A non-serious AE is any AE which does not fulfil the definition of an SAE.

Severity Assessment Definitions:

- Mild: Transient symptoms, no interference with the subject's daily activities
- Moderate: Marked symptoms, moderate interference with the subject's daily activities
- Severe: Considerable interference with the subject's daily activities, unacceptable

Relationship to study medication Assessment Definitions:

- Probable: Good reasons and sufficient documentation to assume a causal relationship
- Possible: A causal relationship is conceivable and cannot be dismissed
- Unlikely: The event is most likely related to an etiology other than the trial product

Outcome Categories and Definitions:

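### The stopping rule for repeated eGFR below 60 has no required re-test, so for a patient who enters at 60 or above the scheduled tests can first meet it at the last visit

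*Combined protocol and SAP*

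**What the plan says.** The Withdrawal Criteria put a renal and a glycaemic condition in one sentence: "Repeated eGFR <60 mL/min/1.73 m² and hypoglycaemic (< 70 mg/dl) episodes will mandate discontinuation of the patient from the study". *Repeated* is given no count, interval or confirmation window.

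The Study Timetable lists "estimated Glomerular Filtration Rate (eGFR) at each visit, baseline (visit t0), 3 (visit t3), and 6 months (visit t6". Visit Procedures adds "The same visit procedures will be repeated after 3 (t3) and 6 (t6) months". The blood tests named in that section are glucose and HbA1c, so the renal schedule rests on the Study Timetable alone. Blood Measurements ties the point-of-care tests to the timetable and adds none.

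The Exclusion Criteria include "Glomerular Filtration Rate (GFR) < 60 mL/min/1.73 m²".

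Three other sections bear on what happens between visits:

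- Follow up of glucose profile sets up weekly contact: "Research coordinator will inform the sponsor investigator on patients' glucose readings". That contact yields glucose values, not eGFR.
- Clinical Laboratory Adverse Event gives examples of active management for an abnormality judged clinically significant: "change of dose, discontinuation of trial product, more frequent follow-up or diagnostic investigation".
- Follow-up of Adverse Events requires events that are serious, severe, or possibly or probably drug-related to be followed until recovery. It names no test and no interval.

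**The concern.** The sponsor chose a renal limit and made action on it mandatory. A mandatory rule needs a measurement that can trigger it in time. Here the rule needs more than one low value, the tests are three months apart, and nothing obliges anyone to test sooner.

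Two things are at stake. The first is safety: a patient whose eGFR at t3 is below the level that would have barred entry may stay on study drug and metformin until t6. The second is consistency and completeness of the data. Two patients with the same t3 value may be handled differently, because only one is re-tested. Removal is from the study, not just from the drug, and Study Hypothesis 1 analyses EAT change at 3 and 6 months. Whether such a patient contributes a 6-month value would then depend on an individual decision to order a test.

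**Working it through.** There is no stated figure to reproduce. The check counts when a second low value can exist.

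**Inputs**

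- Scheduled eGFR tests: t0, t3, t6 (Study Timetable). Taking 3 months as 91 days and 6 months as 182 days, these fall on days 0, 91 and 182.
- Low values needed: 2. This is the smallest count that *repeated* can mean; the plan gives none.
- Entry: GFR below 60 excluded (Exclusion Criteria).
- Last scheduled visit: t6, day 182 (Visit Procedures).

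**Formula.** Days left when the rule is met = 182 − (day of the second low value).

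| Case | Low values | Rule met | Days left |
|---|---|---|---|
| A. Enters at 60 or above, low by t3 and still low at t6, scheduled tests only | days 91 and 182 | day 182 | 182 − 182 = 0 |
| B. Enters at 60 or above, falls below 60 after t3, scheduled tests only | day 182 only | not met | none |
| C. Judged eligible on an earlier value, but low at t0 and t3 | days 0 and 91 | day 91 | 182 − 91 = 91 |
| D1. Low at t3, unscheduled repeat low 1 week later | days 91 and 98 | day 98 | 182 − 98 = 84 (12 weeks) |
| D2. As D1, repeat at 2 weeks | days 91 and 105 | day 105 | 182 − 105 = 77 (11 weeks) |
| D3. As D1, repeat at 4 weeks | days 91 and 119 | day 119 | 182 − 119 = 63 (9 weeks) |

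The wait from a low t3 value to the next scheduled test is 182 − 91 = 91 days, or 13 weeks.

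Cases A and B are what the written schedule delivers for a patient who meets the entry criterion at baseline. Case C needs a patient eligible on one GFR and low on another at t0; the plan neither dates the eligibility GFR nor says what follows a low t0 value. Cases D1 to D3 need a test that the plan does not require. Their intervals are illustrative.

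**The case against.** The strongest reply is that *repeated* means low on repeat testing in ordinary clinical use, so a prompt re-test is implied and the rule can act soon after t3. That may well be the intent. But the text gives no instruction or interval, so the reading rests on the investigator, and the remedy is still to write it down.

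A second reply is that the adverse event sections already cover this. Once a low eGFR is judged a clinically significant laboratory event, closer follow-up is listed as an option, and follow-up of the event is required. This stands in part: the plan does provide a route to an earlier test. The route depends on a judgement about significance, and no time is set. The plan also says that study medication follows current labelling. The label is not among the documents, so whether it adds renal instructions cannot be checked.

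A reader might infer that the rule can never act before month 6, or that it can spare no treatment at all. The documents do not support that. Case C would meet the rule at t3, and an unscheduled repeat could meet it soon after. The zero in case A holds only for a patient who enters at 60 or above and has scheduled tests alone.

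A reader might also infer that many patients are exposed, or that dapagliflozin itself lowers eGFR. The documents give no rate of low values. The rule applies to both arms, and the point does not depend on a drug effect. Entry is limited to patients under 65 with GFR of at least 60 and no signs of hypovolemia.

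Finally, on the scheduled tests alone this rule costs no 6-month EAT, because it is met at t6 or not at all. That is correct. The loss arises when a repeat brings the stop forward, so a required re-test has to come with continued follow-up.

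**Conclusion.** The point holds in limited form and should be corrected. For a patient who enters at 60 or above, the scheduled eGFR tests can first meet the stopping rule at t6, the last visit. A decline that begins after t3 never meets it on those tests. A patient low at t3 may stay on study drug for about 91 more days, and any earlier stop depends on a re-test that the plan permits but does not require.

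This rests on two assumptions: that *repeated* needs at least two low values, and that the t0 value is 60 or above, as the exclusion intends. The number of patients affected is unknown. The point concerns only the renal condition; the hypoglycaemia condition can act between visits through home monitoring and weekly tracking.

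**What to change.** In the Withdrawal Criteria:

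1. State that any post-baseline eGFR below 60 is repeated within a fixed window, for example 2 weeks, in both arms.
2. State that a second value below 60 stops the study drug, with metformin reviewed by the treating clinician.
3. For these patients, replace removal from the study with stopping the study drug. Ask them to attend the remaining visits, including the t6 echocardiogram, so that 6-month EAT is kept.
4. Have eGFR results handled by staff who do not read the echocardiograms, in line with the blinding of both readers to clinical data in the section on reliability of the EAT measurement.

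The two-week window is a suggestion. With a repeat 1 to 4 weeks after a low t3 value, the rule could act 12 to 9 weeks before t6.

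The cost is one extra point-of-care test per low value. Some patients would stop the study drug earlier than now, and their t6 EAT would be measured off drug.

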The risks to patients are extremely minimal in this study. There is a theoretical small increased risk of hypoglycaemic events in the Dapagliflozin + metformin group. There are no other foreseen risks to participants involved in the study. Patients will be required to remove their shirts for echocardiographic evaluation and may feel embarrassed. In addition, the patient may worry that their participation might be disclosed in a weight loss program. Patients will be informed of the echocardiography procedure prior to consenting. There may be some embarrassment from having their waist and hips measured three times throughout the course of a year. Participants

would undergo blood test regardless their participation in the study. The researcher assistant will be advised of any required sensitivity towards participating members

Other Ethical considerations

The study has been submitted to the University of Miami local institutional review board (IRB). Final approval is pending, but highly anticipated. The study will be conducted in accordance with the Declaration of Helsinki. The study will be conducted in accordance with the ICH GCP guidelines. The sponsor-investigator will comply with all applicable regulatory and legal requirements, ICH GCP guidelines and the Declaration of Helsinki in obtaining and documenting the informed consent.

STUDY SCHEDULE:

Planned recruitment period: 1 year

Expected milestones:

- start of study: 01/01/2015
- first patient first visit 01/01/2015
- last patient last visit 12/01/2016
- Planned completion of integrated final study report 01/1/2017

STUDY DRUGS AND MATERIALS:

Study medication

FARXIGA (Dapagliflozin) is SGLT2 inhibitor indicated as an adjunct to diet and exercise to improve glycemic control in adults with type 2 diabetes mellitus

Study Medication supply

Farxiga will be supplied to each study subjects by Astra Zeneca

Labelling of Study Medication

No IND is required. Study medication will be in accordance to current labelling.

Storage and Drug Accountability of Study Medication

The sponsor-investigator will ensure the availability of proper storage conditions and record and evaluate the temperature.

Randomization

This will be an open randomized study. The method of allocation generation will be a computerized random-number generator. The sequence will be generated by the process of restricted randomization. This has greater potential benefit in small trials, as in the present study.

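### The withdrawal rule ends study participation rather than study drug alone, so if either trigger suffices a removed patient's remaining EAT echocardiograms would be lost

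*Combined protocol and SAP*

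**What the plan says.** Withdrawal Criteria names two triggers in one sentence: repeated eGFR below 60 mL/min/1.73 m² and hypoglycaemic (below 70 mg/dl) "episodes will mandate discontinuation of the patient from the study". Stopping study drug is not mentioned as a separate step, here or elsewhere.

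Other relevant text:

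- **Endpoint and visits.** EAT is the primary endpoint (Endpoints) and is measured at baseline, t3 and t6. Visit Procedures says: "The same visit procedures will be repeated after 3 (t3) and 6 (t6) months".
- **Comparison.** Study Design: "Individuals will be randomized in two groups of 50 patients". Study Hypothesis 1 compares the F and M groups with a baseline-adjusted model. Statistical Considerations gives no analysis set and no handling of missing values.
- **Glucose monitoring.** "Study patients will be advised to monitor their capillary glucose twice daily, fasting in the morning and post-prandially". Then: "Glucose profile will be tracked weekly by the research coordinator" (Follow up of glucose profile).
- **Expected imbalance.** Protections against Risk: "There is a theoretical small increased risk of hypoglycaemic events in the Dapagliflozin + metformin group".
- **After an event.** Serious, severe or possibly/probably related adverse events "will be followed until the subject has recovered and all queries have been resolved" (Follow-up of Adverse Events). This is safety follow-up and includes no echocardiogram.

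**The concern.** Removal depends on something that happens after randomisation and that the protocol itself links, if weakly, to the active arm. If removed patients are not measured again, the F versus M comparison rests on those who stayed. The groups then compared may no longer be the groups that were randomised.

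A patient removed before t3 has no post-baseline EAT value, so no change from baseline can be calculated. Values never collected cannot be recovered by any later analysis. Stopping a drug for safety does not require giving up an echocardiogram that is already scheduled.

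**Working it through.** **1. The plan's own figure.** Statistical Considerations states 80% power for 1.2 mm (15% of 8 mm), two-sided 0.05, with 50 per group. It reproduces in two ways by normal approximation:

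- Before-after in one arm, SD 3: 1.2 / (3/√50) = 2.83; Φ(2.83 − 1.96) = 80.7%.
- Between arms, SD 2, 45 per arm (10% loss): 1.2 / (2√(2/45)) = 2.85; Φ(2.85 − 1.96) = 81.2%.

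SD 2 is used below because the plan expects about 2 for the change. (Between arms with SD 3 and 50 per arm, power is 51.6%; that is a separate matter.)

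**2. What each reading of the rule loses.**

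| Reading | EAT data at risk |
|---|---|
| Either trigger suffices; hypoglycaemia need not recur | t3 and t6 if removed before t3; t6 only if removed between t3 and t6 |
| Either suffices; *repeated* also governs hypoglycaemia | Same pattern, fewer patients |
| Both triggers required | Fewest patients |

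The hypoglycaemia trigger can act early. If every advised self-test is done, there are 2 × 7 × 13 = 182 readings in the 13 weeks before t3. That counts opportunities, not removals.

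The eGFR trigger is slower. GFR below 60 is excluded at entry and eGFR is scheduled only at t0, t3 and t6. On scheduled tests alone, a repeated low value is first reached at t6, when EAT is also measured. Unscheduled tests could bring it forward: Clinical Laboratory Adverse Event allows for more frequent follow-up.

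**3. Possible shift in the arm difference.** No removal rate is given, so these inputs are assumed. The 10% end borrows the ceiling for attrition from all causes in Compliance and Retention Strategy; 1.2 mm is the target effect.

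Shift = (fraction of F removed × difference) − (fraction of M removed × difference), where difference means removed minus retained patients.

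- F only: 0.05 × 1.2 = 0.06 mm; 0.10 × 1.2 = 0.12 mm. As a share of the target: 0.06/1.2 = 5%; 0.12/1.2 = 10%.
- Half as many removed from M, same difference: 0.06 − 0.03 = 0.03 mm; 0.12 − 0.06 = 0.06 mm.
- Equal loss, equal difference: 0.

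For scale, the standard error of the arm difference is 2 × √(2/50) = 0.40 mm.

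**4. Cost of keeping these patients.** Suppose 5-10% of the F arm stop early and show no effect. The as-randomised difference is then 1.2 − 0.06 = 1.14 mm or 1.2 − 0.12 = 1.08 mm. Power by two-sample t-test (noncentral t), SD 2, two-sided 0.05:

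| Scenario | Patients F/M | Difference | Power |
|---|---|---|---|
| No removals | 50/50 | 1.20 mm | 84.4% |
| 5% stop, kept | 50/50 | 1.14 mm | 80.6% |
| 10% stop, kept | 50/50 | 1.08 mm | 76.2% |
| 5% dropped | 47.5/50 | 1.20 mm | 83.4% |
| 10% dropped | 45/50 | 1.20 mm | 82.4% |

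**The case against.** **Few patients may meet the rule.** The fasting target is 80-140 mg/dl, so its floor is above the threshold. Up-titration is conditional on safety, and weekly readings reach the sponsor-investigator, who may be able to act before episodes recur. The increase on dapagliflozin is called theoretical and small. All of this stands, and it is why the effect is judged probably small.

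**Bias and dilution are partly one quantity.** If removed patients would have shown no effect, the 0.06-0.12 mm shift in step 3 is the same 0.06-0.12 mm dilution as in step 4. Whether keeping them removes bias or loses signal depends on whether the target is the as-randomised or the on-treatment effect. The primary objective asks about treatment with dapagliflozin, which is compatible with the latter. This stands too. But the rule as written forecloses the as-randomised analysis for these patients, whereas collecting the data leaves both possible.

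**Stronger readings that the documents do not support.** A reader might infer that one reading below 70 mg/dl always ends participation, or that every removed patient loses both echocardiograms. The word *repeated* may govern both triggers, both may be required, and a patient removed after t3 has already given that value. A reader might also reach a shift of 0.10 × 2.0 = 0.20 mm, or 17% of the target. That combines three extremes: 10% of the F arm removed under this rule alone, when attrition from all causes is put below 10%; no placebo removals; and a difference equal to the full 25% drug effect. Nor can it be said that the eGFR trigger costs at most t6, since unscheduled tests are possible.

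**Conclusion.** The point holds in conditional form. The rule ends participation, no provision keeps the later echocardiograms, and on the natural reading remaining primary-endpoint data would be lost. The loss of visits is inferred from the wording of the rule and the absence of any retained-visit provision; it is not stated outright.

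The loss may differ by arm and could slightly bias the F versus M comparison. Neither size nor direction follows from the documents. The illustrative 0.06-0.12 mm is at most 0.12/0.40 = 0.3 of a standard error. It rests on assumed removal of 5-10% from the F arm only and an assumed 1.2 mm difference, and it falls to about 0 with equal loss and equal difference. A reader might infer that the trial's result is compromised or tilted towards dapagliflozin; nothing in the documents shows that. This is a worthwhile, inexpensive improvement, held with medium confidence.

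**What to change.** - Reword the rule so that, at the same thresholds, study drug is discontinued. State whether either trigger suffices and whether hypoglycaemia must recur.
- Keep these patients in the planned t3 and t6 echocardiogram visits unless they withdraw consent.
- Include their data by assigned arm in the planned baseline-adjusted comparison.
- Report drug discontinuations by arm and reason, with an on-treatment analysis as sensitivity.

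Cost: a wording change, with no new visit or procedure and no change to when drug is stopped for safety. The as-randomised estimate is modestly diluted. In the step 4 scenario, power is about 81-76% with these patients kept against about 83-82% with them dropped, so at 10% it falls below the planned 80%. The on-treatment analysis still gives the undiluted estimate, though it remains open to the selection described above.
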